#### 4.3.2. Adverse Events

##### Primary analysis

In primary analysis, AEs will be summarized for on-treatment period, unless otherwise specified. The definition of on-treatment period:

- Subjects who did not withdraw early from IP:  
Event onset date is on/after IP start date & on/before Week 12 Date.  
(IP Start Date  $\leq$  Event Start Date  $\leq$  Week 12 Date)
- Subjects who withdrew early from IP:  
Event onset date is on/after IP start date & on/before Early Withdrawal Date.  
(IP Start Date  $\leq$  Event Start Date  $\leq$  Early Withdrawal Date)

AEs with partial or missing start and/or stop dates will be assumed to be on-treatment unless there is evidence through comparison of partial dates to suggest otherwise.

The duration of the AE will be calculated as follows:

$$\text{Duration of AE (days)} = \text{Date of AE resolution} - \text{AE start date} + 1.$$

If the AE is ongoing the duration will be left blank and no imputation will be done.

Common AEs and common non-serious AEs will be defined as two or more subjects experiencing the event.

An overall summary of AEs will be presented showing the number and percent of subjects with at least one: AE, related AE, serious AE (SAE), severe AE, serious and/or severe AE, AE resulting in study agent discontinuation, and deaths during on-treatment period:

- Overview of all AEs

The number and percentage of subjects experiencing an AE and the incidence of AEs will be summarized for each of the following AE categories:

- All AEs (by SOC; by SOC and PT; by PT only)
- Serious AEs (by SOC; by SOC and PT; by PT only)
- Severe AEs (by SOC; by SOC and PT; by PT only)
- Study Agent Related AEs (by SOC; by SOC and PT; by PT only)

- AEs Resulting in Study Agent Discontinuation (by SOC; by SOC and PT; by PT only)
- Common AEs (by SOC and PT)
- Non-Serious AEs (by SOC and PT)
- Common Non-Serious AEs (by SOC and PT)
- Study Agent Related Serious AEs (by SOC and PT)
- Study Agent Related Non-Serious AEs (by SOC and PT)
- Fatal Serious AEs (by SOC and PT)
- Non-Fatal Serious AEs (by SOC and PT)
- Study Agent Related Non-Fatal Serious AEs (by SOC and PT)

A summary of AEs by SOC and severity will also be provided. For this display, the number and percentage of subjects will be summarized as mild, moderate, or severe based on the maximum severity observed across all PTs within the SOC during the specified study period for a given subject.

Summaries of AEs and drug related AEs by SOC, PT and severity will also be provided. The number and percentage of subjects will be summarized as mild, moderate, or severe based on the maximum severity observed within each PT, and within each SOC, during the specified study period.

The table for all AEs by SOC and PT will be repeated for body weight. See Section [4.4.1](#) for details on the subgroup categories.

A listing of all AEs will be presented, including duration and study day.

A listing for all SAEs will be produced.

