1.3.3. Body weight ≥15 kg - <30kg, Dose 200 mg Q2W

Site Visit	V1	V2	V3	V4	V5	V6	V7	V8	V9	V10	V11	V12	
Procedure	Screening	Treatment Period (12 weeks)										Follow-Up Period ^{1,2}	
Study Day/Week	-35 days	Day 1	Day 4±1	Day 15±2	Day 29±2	Day 43±2	Day 57±2	Day 71±1	Day 74±1	Day 85±2 /EW ¹	8-Week ±7-Day Follow-up ¹	16-Week±7-Day Follow-up ^{1,2}	
		Wk 0		Wk 2	Wk 4	Wk 6	Wk 8	Wk 10	Wk 12				
Informed consent	X												
Inclusion and exclusion criteria	X												
Demography	X												
Medical history	X												
Safety Assessments													
Concomitant Medication	X	X		X	X	X	X	X		X	X		

CONFIDENTIAL

217091
Protocol Amendment 2

Site Visit	V1	V2	V3	V4	V5	V6	V7	V8	V9	V10	V11	V12
Procedure	Screening	Treatment Period (12 weeks)									Follow-Up Period ^{1,2}	
Study Day/Week	-35 days	Day 1	Day 4±1	Day 15±2	Day 29±2	Day 43±2	Day 57±2	Day 71±1	Day 74±1	Day 85±2 /EW ¹	8-Week ±7-Day Follow-up ¹	16-Week±7-Day Follow-up ^{1,2}
		Wk 0		Wk 2	Wk 4	Wk 6	Wk 8	Wk 10		Wk 12		
Symptom Driven Physical Exam ³	X	X			X		X			X	X	
Vital Signs	X	X	X	X	X	X	X	X	X	X	X	
Weight	X	X ⁶		X	X	X	X	X		X	X	
Height		X			X		X			X	X	
12-Lead ECG	X											
Adverse Events		X		X	X	X	X	X		X	X	X
Serious Adverse Events		X		X	X	X	X	X		X	X	X
Device Incidents malfunctions		X		X	X	X	X	X		X		
Laboratory Assessments												
Haematology	X ⁵	X ⁵			X		X			X	X	
Chemistry	X ⁵	X ⁵			X		X			X	X	
Urinalysis	X ⁵	X ⁵			X		X			X	X	
Pregnancy Test ⁴	X ⁵	X ⁵			X		X			X	X	
IgA, IgG and IgM	X	X ⁵			X		X			X	X	
Belimumab Administration and PK Sampling												
PK Sampling	X ⁷	X ⁸	X ¹⁰	X ^{8, 11}				X ⁸	X	X		
Administration of Belimumab		X ⁹		X ⁹	X	X	X	X				

ECG: Electrocardiogram, IgA: Immunoglobulin A, IgG: Immunoglobulin G, IgM: Immunoglobulin M, PK: Pharmacokinetic. Note:

CONFIDENTIAL

217091
Protocol Amendment 2

1. 8-week and 16-week follow-up is required for participants who withdraw from study treatment prior to Week 12 (Month 3) or completed 12 weeks of treatment. For participants who withdraw from treatment prior to Week 12 (Month 3), in addition to the 8-week and 16-week follow-up visit and assessments, an early withdrawal visit (EW) should be completed within 4 weeks of the decision to withdraw. The EW visit requires identical assessments and procedures to the Week 12 visit (Month 3).

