Rationale for estimand: Interest lies in the exposure parameters when participants have actually taken study medication irrespective of interruption of study medication. For using of prohibited medications or therapies, the while-on-treatment strategy is motivated by the potential confounding of PK data after using prohibited medications or therapies.

For estimand strategy in secondary endpoint. The estimand is described by the following attributes:

Population	Chinese paediatric participants 5-17 years of age with systemic lupus erythematosus (SLE) who have previously been treated with IV belimumab
Treatment	
 • Repeat doses of 200mg belimumab administered subcutaneously (SC) over 12 weeks on a background of standard of care therapy
Endpoints	
 • Occurrence of adverse events, serious adverse events and adverse events of special interest through Week 12.
Summary Measure	
 • Frequency and percentage
Intercurrent events and strategies	
 • Discontinuation of study medication, addressed with while-on-treatment strategy. Safety data in the 12-week on-treatment period will be used in analysis. The definition of on-treatment period will be provided in reporting and analysis plan (RAP).

Rationale for Estimand: This attempts to estimate on-treatment safety effects likely to be attributable to the drug.

In addition to estimand strategy in secondary endpoint, an additional analysis will be performed based on all safety data including 12-week on-treatment period and 16-week post-treatment follow-up period.

Further details on estimand strategy will be provided in the RAP.

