7.2. Participant Discontinuation/Withdrawal from the Study

The legal guardian and the paediatric participant have the right to withdraw permission (consent or assent, respectively) at any time during the study. If the study staff identify any reluctance in the legal guardian or paediatric participant (e.g., signs of verbal or physical dissent) about continued participation in the study, the paediatric participant's continuation in the study should be re-evaluated. The same principles that govern permission/assent/consent also govern its withdrawal.

A participant will be withdrawn from the study for any of the following reasons:

- Withdrawal of consent or assent if applicable (A paediatric participant's dissent should be respected.)
- A participant may withdraw from the study at any time at his/her own request or may be withdrawn at any time at the discretion of the investigator for safety, behavioural, or compliance reasons. This is expected to be uncommon.
- At the time of discontinuing from the study, if possible, an early discontinuation visit should be conducted, as shown in the SoA. See SoA for data to be collected at the time of study discontinuation and follow-up and for any further evaluations that need to be completed.
- The participant will be permanently discontinued from the study intervention and the study at that time.
- If the participant withdraws consent for disclosure of future information, the sponsor may retain and continue to use any data collected before such a withdrawal of consent.
- If a participant withdraws from the study, he/she may request destruction of any samples taken and not tested, and the investigator must document this in the site study records.

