7.3. Lost to Follow Up

A participant will be considered lost to follow-up if he/she repeatedly fails to return for scheduled visits and is unable to be contacted by the study site.

The following actions must be taken if a participant fail to return to the clinic for a required study visit:

- The site must attempt to contact the participant and reschedule the missed visit as soon as possible, counsel the participant on the importance of maintaining the

assigned visit schedule and ascertain whether the participant wishes to and/or should continue in the study.

- Before a participant is deemed lost to follow-up, the investigator or designee must make every effort to regain contact with the participant (where possible, 3 telephone calls and, if necessary, a certified letter to the participant's last known mailing address or local equivalent methods). These contact attempts should be documented in the participant's medical record.
- Should the participant continue to be unreachable, he/she will be considered to have withdrawn from the study.

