### 4.3. Safety Analyses

The safety analyses will be based on the ITT Analysis Set, unless otherwise specified.

For estimand strategy in safety. The estimand is described by the following attributes:

Population	Chinese paediatric participants 5-17 years of age with systemic lupus erythematosus (SLE) who have previously been treated with IV belimumab
Treatment	
 
Repeat doses of 200mg belimumab administered subcutaneously (SC) over 12 weeks on a background of standard of care therapy
 

Endpoints	
 
Occurrence of adverse events, serious adverse events and adverse events of special interest through Week 12.
 

Summary Measure	
 
Frequency and percentage
 

Intercurrent events and strategies	
 
Discontinuation of study medication, addressed with while-on-treatment strategy. Safety data in the 12-week on-treatment period will be used in analysis.
 

Rationale for Estimand: This attempts to estimate on-treatment safety effects likely to be attributable to the drug.

In addition to estimand strategy in secondary endpoint, an additional analysis will be performed based on all safety data including 12-week on-treatment period and 16-week post-treatment follow-up period.

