## 6.2. Appendix 2 Data Derivations Rule

### 6.2.1. Study Period

Assessments and events will be classified according to the time of occurrence relative to the study intervention period.

Treatment period	Definition
Pre-Treatment	Event start date < IP start date
On-Treatment	IP start date ≤ Event start date ≤ Week 12 Date or Early Withdrawal Date
Post-Treatment	Event start date > Week 12 Date or Early Withdrawal Date

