### 6.2.3. Assessment Window

Different body weight will have different schedule of visits. Therefore, the data will be analysed by the analysis timepoint (Week 0, Week 2, Week 4, Week 6, Week 8, Week 10, Week 12, 8-week Follow-up and 16-week Follow-up).

Early withdrawal and unscheduled visits will be slotted to the appropriate planned visit. The assigned analysis timepoint will be based on the interval in which the Study Day for the early withdrawal or unscheduled visit falls according to intervals provided below.

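### Does the undefined early-withdrawal date that closes the SAP's on-treatment period call for a change to the plan?

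*SAP*

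**What the plan says.** Protocol section 3 leaves the definition of the on-treatment period to the analysis plan. SAP 4.3.2 supplies it. Participants who stay on study drug are covered from first dose to the Week 12 date. For those who stop early the condition is "Event onset date is on/after IP start date & on/before Early Withdrawal Date". SAP 6.2.1 repeats the two end dates and introduces them with "Assessments and events will be classified according to the time of occurrence relative to the study intervention period".

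The SAP's safety estimand (4.3) limits the endpoint to Week 12 and says "Safety data in the 12-week on-treatment period will be used in analysis".

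On the visit itself, note 1 to the Protocol's Schedule of Activities says "an early withdrawal visit (EW) should be completed within 4 weeks of the decision to withdraw". Protocol 7.1 and 8.1.4 make the visit a requirement. Protocol 7.2 is softer: "At the time of discontinuing from the study, if possible, an early discontinuation visit should be conducted, as shown in the SoA". Protocol 7.3 adds, for participants who cannot be contacted, "Should the participant continue to be unreachable, he/she will be considered to have withdrawn from the study".

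For by-week summaries, SAP 6.2.3 states "Early withdrawal and unscheduled visits will be slotted to the appropriate planned visit", with the slot chosen by study day. The last intervals close on Day 87 (weekly dosing), Day 84 (every 10 days) and Day 90 (every 2 weeks). The follow-up rows have a target day but no interval.

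**The concern.** The end date decides which of a withdrawer's events enter the primary safety tables, and it is not defined. The visit is a plausible reading, because it parallels the Week 12 date and the Schedule of Activities puts the two in one column. Three difficulties follow from that reading:

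- The operational rule has no Week 12 limit, although the estimand has one.
- A participant who never attends the visit has no end date. An event then meets neither the on-treatment nor the post-treatment condition in SAP 6.2.1. The SAP's rules for incomplete dates cover adverse events, medications and medical history, not this reference date.
- A visit after the last slotting interval has no place in the by-week laboratory and vital-sign summaries.

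In an open-label study, a cut-off chosen after the events are known would be unwelcome.

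**Working it through.** **Inputs.** All triplets are in the order weekly, every 10 days, every 2 weeks.

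- Week 12 day: 85, 81, 85 (Protocol 1.3).
- Maximum delay to the early-withdrawal visit: 28 days (Protocol 1.3, note 1).
- End of the last slotting interval: Day 87, 84, 90 (SAP 6.2.3).
- Planned N = 17 and withdrawal rate 20% (Protocol 9.5, SAP 5).

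**The plan's own figure.** 14 × 1.20 = 16.8, rounded up to 17. (Dividing instead, 14 / 0.80 = 17.5, gives 18. The difference has no bearing here.)

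**Participants concerned.** 17 × 0.20 = 3.4, so about 3. One participant is 1/17 = 5.9 percentage points.

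**Reading A: the date of withdrawal from study drug, or of the decision to stop.** The SAP rule is addressed to participants who withdrew early from study drug, so this reading is at least as natural as the visit. An early stop comes before Week 12. Even a decision on the day before falls on Day 84, 80 or 84, so the period cannot pass Week 12. The first difficulty does not arise.

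**Reading B: the visit date.** The period passes the Week 12 day only if decision day + 28 exceeds it:

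- 85 − 28 = 57, so a decision on Day 58 or later (weekly)
- 81 − 28 = 53, so Day 54 or later (every 10 days)
- 85 − 28 = 57, so Day 58 or later (every 2 weeks)

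It also needs a visit near the end of the 4-week allowance. Since the decision precedes Week 12, the overrun is less than 28 days if that allowance is kept. I give no tighter maximum, because the documents do not fix the latest day on which an early stop can be decided, and Protocol 6.4.2 lets some doses be given late.

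**Events that depend on the reading.** Between A and B, only events that start after the date used in A and no later than the visit change class. Events that start on or before the decision to stop are on-treatment under either the decision or the visit reading.

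**No visit.** Under A, the second difficulty largely goes away. Unreachable participants count as withdrawn, and SAP 6.1.1 already tabulates withdrawals by study visit and by reason, so withdrawal has to be recorded. The case report form is not among the documents, so the exact field is an assumption.

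**Slotting.** A visit 28 days after the decision falls beyond the last interval if the decision is on Day 60, 57 or 63 or later (87 − 28 + 1 = 60; 84 − 28 + 1 = 57; 90 − 28 + 1 = 63). The values remain in the laboratory and vital-sign listings (SAP 4.3.3.1 and 4.3.3.2).

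**What does not depend on the date.** SAP 4.3.2 repeats the overview and the tables of all, severe, serious and related events, and of events by severity, over treatment plus 16 weeks of follow-up. SAP 4.3.2.1 does the same for the overall summary and listing of events of special interest. The listing of all adverse events gives study day, so a reader can apply any cut-off. The pharmacokinetic estimand in Protocol section 3 sets its own rule for samples from the early-withdrawal visit and does not use this SAP term.

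**The case for a change.** The strongest case for acting is that a programmer implements the operational rule and not the estimand, and here the rule omits the estimand's limit. The all-period tables are not a full replacement either. Events leading to discontinuation by system organ class and preferred term, and the body-weight adverse-event table, are planned for the on-treatment period only. The post-treatment listing depends on the same boundary. A common event is one seen in two or more participants, so reclassifying one person can add or remove a row. Defining the date would cost a sentence.

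Much of this is correct. The term is undefined, no fallback is named, and the slotting intervals do stop where stated. A line in the programming specification, written before the tables are run, would be good practice.

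It does not show that a conclusion is at risk. The Week 12 limit is in the SAP's own estimand, so an analyst who meets a late visit has a stated principle to follow. An event that causes discontinuation starts no later than the decision to stop, so it stays on-treatment under the decision or the visit reading. A row gained or lost in a table of common events, in a single arm of about 17, supports no comparison or test.

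A rewrite can also introduce its own inconsistency. Capping events at Day 87, 84 or 90 would give withdrawers in the two less frequent schedules a later limit than completers, whose visit windows close on Day 83 (81 + 2) and Day 87 (85 + 2). Keeping later laboratory values on-treatment while capping events would split the single period that SAP 6.2.1 uses for both.

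**Conclusion.** The gap is real, but it is one of detail. Analysts would choose a recorded date, name a substitute for a missed visit and respect the Week 12 limit already in the estimand, all before programming. The effect is confined to a descriptive secondary endpoint and to about 3 of 17 participants at 5.9 percentage points each. Even among these, it reaches only those with an event between stopping and the visit, or with no visit at all. The documents do not say how many will miss the visit, and I put no figure on it.

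This rests on two assumptions: that the case report form records a withdrawal date, and that the date is fixed before the tables are produced. On those terms the safety conclusion would be the same under any sensible reading, and no change to the plan is needed.

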### **Additional analysis**

All subjects will be followed for safety at 16-week post-treatment follow-up period. In addition to the primary analysis for on-treatment period, overview of all AEs showing the number and percent of subjects with at least one: AE, related AE, serious AE (SAE), severe AE, serious and/or severe AE, AE resulting in study agent discontinuation, and deaths; and the following summary tables will be produced for all AEs including 12-week on-treatment period and 16-week post-treatment follow-up period:

- All AEs (by SOC and PT)
- Severe AEs (by SOC and PT)
- Serious AEs (by SOC and PT)
- Study Agent Related AEs (by SOC and PT)

Summary of AEs by SOC, PT and severity will also be provided. The number and percentage of subjects will be summarized as mild, moderate, or severe based on the maximum severity observed within each PT, and within each SOC.

The following listings will be produced:

- Listing of all AEs in 16-week post-treatment follow-up period

#### **4.3.2.1. Adverse Events of Special Interest**

In primary analysis, AESIs will be summarized for on-treatment period, unless otherwise specified.

To ensure consistency across belimumab studies, AESI will be defined per the version of the Program Safety Analysis Plan (PSAP) and MedDRA in effect at the time of data base release (DBR).

The Benlysta PSAP has been developed to include an adverse event of special interest (AESI) analysis for consistent reporting across belimumab studies. Categorizations for the AESIs are defined in the PSAP.

An overall summary of AESIs will be presented and each specific category of AESI will be presented separately by PT. The number and percentage of subjects with at least one occurrence and the number of events of the following AESIs will be provided.

The following AESI will be identified and adjudicated as detailed in the Program Safety Analysis Plan (PSAP).

Adverse Events
Adverse Events of Special Interest (AESI)
AESI will be defined per the version of the PSAP/MedDRA in effect at the time of DBR.
Malignant Neoplasms 

• Malignancies Excluding non-melanoma skin cancer (NMSC)

• Malignancies Including NMSC

• Solid Tumour

• Hematologic

• Skin (All)

• NMSC

• Excluding NMSC

• Tumours of unspecified malignancy adjudicated as malignant per GSK

Post-Injection Systemic Reactions (PISR) 

• PISR per Anaphylactic Reaction Customized MedDRA Query (CMQ) narrow search

• Serious PISR per Anaphylactic Reaction Customized MedDRA Query (CMQ) narrow search

• PISR per Anaphylactic Reaction CMQ broad search

**Adverse Events****Adverse Events of Special Interest (AESI)**

- Serious PISR per Anaphylactic Reaction CMQ broad search
- PISR per Anaphylactic Reaction CMQ algorithmic search
- Serious PISR per Anaphylactic Reaction CMQ algorithmic search

All Infections of Special Interest (Opportunistic Infections (OI), Herpes Zoster (HZ), Tuberculosis (TB), And Sepsis; All and Serious, separately)

- All opportunistic infections (OI) per GSK adjudication
- OI per GSK adjudication excluding Tuberculosis and Herpes Zoster
- Active Tuberculosis
  - Non-Opportunistic
  - Opportunistic
- Herpes Zoster
  - Non-Opportunistic
  - Opportunistic
    - Recurrent
    - Disseminated
- Sepsis

Depression (including mood disorders and anxiety)/suicide/self-injury (All and Serious, separately)

- Depression (including mood disorders and anxiety) (excluding suicide and self-injury)
- Suicide/self-injury
- Serious suicide/self-injury per GSK adjudication
  - Suicidal Behavior
    - Completed Suicide
  - Suicidal Ideation
  - Self-injurious Behavior without Suicidal Intent

## Deaths

Malignant neoplasm events identified as “tumours of unspecified malignancy” will be reviewed for classification as malignant per GSK adjudication and will be presented by category and PT.

Post-injection systemic reactions and serious post- injection systemic reactions will be presented using different definitions as indicated above. These will be presented by category and PT.

Infection AESIs will be presented by Category and PT for all infections and for infections leading to study treatment discontinuation.

Depression, suicide and self-injury as defined in the PSAP will be presented by Category and PT.

Death will be presented by Category and PT.

Summaries of post-injection systemic reactions that occur on the day of an injection or within 3 days after an injection will be presented by the first six injection and over all injections, and PT for the following:

- Post-Injection Systemic Reactions per Anaphylactic Reaction CMQ broad search (on the day of the injection or within 3 days after the Belimumab injection) by PT in the first six injection.
- Serious Post-Injection Systemic Reactions per Anaphylactic Reaction CMQ broad search (on the day of the injection or within 3 days after the Belimumab injection) by PT in the first six injections.

